2.1 OBJECTIVES AND SCIENTIFIC AIMS

Primary objective:

The primary objective of this study is to assess patency of biliary drainage. In patients with plastic percutaneous drains this is defined as ability to remove plastic biliary drains within 1.5 months of the IRE procedure without need for reinsertion of a drain or stent. For patients with metal stents in place the definition of patent biliary drainage is 4-months without cholangitis post IRE procedure.

Secondary objective:

The secondary outcomes of interest are

- Duration of hospital stay
- Complications
- Quality of life
- Tumor response on CT imaging and blood biomarker response
- Time between IRE and start of palliative chemotherapy
- Duration of palliative chemotherapy
- Progression-free and overall survival
- Success rate of completing IRE (defined as percentage of planned pulses completed)

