6.1 CRITERIA FOR SUBJECT ELIGIBILITY

The study population consists of 20 adult patients who are diagnosed with locally advanced, unresectable PHC. Unresectability will be established either preoperatively, based on imaging and other preoperative testing, or intraoperatively in patients undergoing planned exploratory laparotomy. Patients will be recruited at the outpatient clinic. In cases of a planned exploratory laparotomy, patients will be asked to participate in the study in case disease is deemed unresectable during surgery. These patients will undergo RE during the same operative session. Patients with unresectable tumors based on imaging at initial visit or preoperative workup, will be asked to participate in the study and receive RE via laparotomy. Prior to surgery, biopsies will be taken to verify perihilar cholangiocarcinoma. Patients with resectable PHC, PHC eligible for liver transplantation or organ metastasized PHC at surgical exploration will be excluded. The subject exclusion criteria outlined below is evaluated per standard of care for the RE procedure and as such is listed in this protocol.

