9.0 TREATMENT/INTERVENTION PLAN

Preoperative biliary drainage

Biliary drainage for malignant hilar strictures or masses is a complex procedure requiring considerable skill and experience. Candidates for IRE who initially present with potentially resectable PHC undergo preoperative biliary drainage as part of the standard preoperative work-up. In the present study, the exact approach of biliary drainage (i.e. endoscopically or percutaneously, specified liver segments, unilateral or bilateral) prior to surgery is decided by surgeon. A metal biliary stent is not considered a contraindication for IRE as long as a no-touch technique is pursued (i.e. IRE electrodes are not in contact with the metal stent).

Antibiotic prophylaxis

Antibiotic prophylaxis will be administered according to the MSKCC's protocol prior to biliary drainage and IRE. Patients will receive one 2g dose of Cefotetan IV, 30-60min prior to surgery. The same antibiotic will be used for the treatment of cholangitis (2g Cefotetan IV every 12 hours). In case of a patient allergy to Cefotetan, patients will receive Clindamycin/Gentamicin as alternative antibiotic treatment.

Intraoperative IRE procedure

Antibiotic prophylaxis is administered prior to the operation. During exploratory laparotomy, resectability of the tumor is assessed by the attending surgeon. When the tumor appears resectable, a resection will be performed. In case of non-nodal (extra)hepatic dissemination of the tumor, no procedure will be performed. In both cases the patients will be excluded from this study. Only when the tumor appears non-resectable, but non-metastasized, an IRE procedure will be performed. The IRE procedure will be performed under ultrasound guidance by the attending surgeon.

NanoKnife® device settings

The NanoKnife® IRE device (AngioDynamics, Queensbury, NY) will be used in this study in normal clinical fashion. This means the machine will be configured to deliver 90 pulses lasting one microsecond each, high-voltage (1500-3000 V) direct current (25-45 A) electrical pulses. Before administering the 90 one-microsecond therapeutic pulses, a test pulse at 270 V is delivered. Typically, 90 pulses will be delivered in 9 sets of 10 pulses between paired unipolar electrodes, with an exposed tip of 1.5-2.0 cm. The voltage setting for each electroporation will

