CT and rvRI scans used for routine clinical care will be used for this protocol. If patients are receiving chemotherapy, a pre-chemotherapy scan will be obtained 4-6 weeks post procedure, as per standard clinical practice. If no chemotherapy is planned a scan at 4-6 weeks will be clinically appropriate to assess disease progression, treatment response, and stent patency. Scans every 4-6 months will be used in patients on and off chemotherapy to evaluate for disease progression, which is consistent with current practices for routine management of patients with PHC. Tumor response is defined as a loss of enhancement for hypervascular tumors and as a lack of persistent tumor rim enhancement for hypovascular tumors on contrast imaging studies. Persistent disease is defined as residual tumor enhancement on the posttreatment imaging studies, and local recurrence is defined as an enhancing tumor within 1cm of an ablation zone.

In order to diagnose complications such as biliary leakage, intra-abdominal abscesses or bleeding, ultrasound and CT are used. When disease progression is expected, a CT is performed to confirm (or refute) the clinical suspicion. This procedure is consistent with normal clinical standards.

Follow up of subjects withdrawn from treatment

Patients withdrawn from treatment will not have undergone the RE procedure and are therefore considered not to have participated in this study. These subjects will receive normal follow-up outside this study.

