- Progression-free and overall survival will be summarized using Kaplan-Meier statistics
- Success rate of completing RE reported as a binomial proportion with a 95% confidence interval

Expected accrual rate, accrual duration, and study duration

Our anticipated accrual rate is approximately 1 patient per month. This accrual rate is based on analysis of potentially eligible patients seen at our Outpatient Clinic in the last 2 years (2016 and 2017). Thus, it should take approximately 1.5 years to accrue the 20 patients needed for the trial. Allowing for 2 months of follow-up to obtain the primary endpoint on the last patient enrolled and 4 months to assemble, analyze and interpret the data the total study duration is projected to be at most 2 years. Patients who consent to the procedure but do not have it will be considered a screen failure. They will be replaced by another patient and their questionnaire data will be removed from the study.

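### Eligible patients opened for IRE who receive no pulses are removed by rule, so the IRE completion rate is overstated whenever such a patient occurs

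*Combined protocol and SAP*

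**What the plan says.** (In several quotes the extracted text prints IRE as RE.)

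- **Replacement rule.** The accrual paragraph of section 14.1 states: "Patients who consent to the procedure but do not have it will be considered a screen failure". It continues: "They will be replaced by another patient and their questionnaire data will be removed from the study". No reason for not having the procedure is distinguished.
- **Status of these patients.** Section 10.0, on subjects withdrawn from treatment, says: "Patients withdrawn from treatment will not have undergone the RE procedure and are therefore considered not to have participated in this study". They are then followed outside the study.
- **Ineligibility found at surgery.** Section 9.0 deals separately with tumours that prove resectable or show non-nodal dissemination: "In both cases the patients will be excluded from this study".
- **Route to treatment.** Under section 6.1, patients known before surgery to be unresectable "will be asked to participate in the study and receive RE via laparotomy". For them the operation is done in order to give IRE.
- **Completion outcome.** Section 2.1 lists "Success rate of completing IRE (defined as percentage of planned pulses completed" among the secondary outcomes. Section 14.1 gives the analysis: "Success rate of completing RE reported as a binomial proportion with a 95% confidence interval".

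**The concern.** At exploration there are three kinds of patient: those found ineligible, those eligible and treated, and those eligible in whom IRE was intended but not delivered. Section 9.0 handles the first two. The third is caught only by the general wording in sections 10.0 and 14.1, which removes and replaces them.

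The protocol's own constraints make this third group possible. Section 3.0 advises against electrodes within 3 mm of central bile ducts. Section 9.0 requires that electrodes do not touch a metal stent, sets inter-electrode distances of 10-24 mm and a maximum angulation of 15°, and plans to record probe replacements for unsatisfactory placement.

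A patient with no pulses delivered has the worst possible result on the completion outcome, yet can never be counted in it. Anyone using the published figure to judge how often IRE can be carried out at the hilum would be misled. Harm from a laparotomy done in order to give IRE would also have no assigned place in the trial's results.

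**Working it through.** **Plan's own figure.** The documents state no expected completion or non-delivery rate, so there is nothing to reproduce. The error rates and stopping probability quoted in section 14.1 play no part in this point.

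**Does any other provision keep these patients?**
- Section 13.0 counts withdrawal before 30 days as a complication. Section 10.0, however, says patients withdrawn from treatment never participated, so section 13.0 does not clearly reach them.
- Section 17.3 starts SAE reporting when the intervention starts. It does not say whether that means the laparotomy or the first pulse.
- No analysis set of attempted patients is defined anywhere.

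**Effect on completion.** Inputs: 20 treated patients (section 14.1); k eligible patients opened for IRE with no pulses delivered (assumed, k = 1 to 3). Suppose all 20 treated patients complete. The plan reports 20/20 = 100% (exact 95% CI 83.2% to 100%). Counting the undelivered patients gives 20/(20 + k):

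| k | Rate | Exact 95% CI | Overstatement |
|---|---|---|---|
| 1 | 20/21 = 95.2% | 76.2% to 99.9% | 4.8 points |
| 2 | 20/22 = 90.9% | 70.8% to 98.9% | 9.1 points |
| 3 | 20/23 = 87.0% | 66.4% to 97.2% | 13.0 points |

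If the outcome is instead read as a mean percentage of planned pulses per patient, with mean c among the treated, the corrected mean is (20 × c + k × 0)/(20 + k) = c × 20/(20 + k). The same factor applies. If only 18 of the 20 complete, the reported 90% becomes 18/21 = 85.7%, 18/22 = 81.8% or 18/23 = 78.3%. The direction is fixed: adding patients at 0% cannot raise the rate.

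**Effect on 30-day safety.** Start from 6 of 20 = 30%, the largest count that meets the safety endpoint, and take k = 2. With 0, 1 or 2 complications among the two undelivered patients, the rate over all attempts is 6/22 = 27.3%, 7/22 = 31.8% or 8/22 = 36.4%. The direction is not fixed.

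**Effect of adding undelivered patients to the interim safety count.** The study stops if 4 or more of the first 8 have an event. At a complication rate of 35%, the binomial probability of 4 or more events is 29.4% with 8 patients at risk. If one of the 8 had no IRE and no event (an assumption), only 7 are at risk and the probability is 20.0%. Leaving the boundary unchanged and adding such patients would weaken it.

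**The case against.** The strongest reply is that the treated population is the declared target. Section 4.3 says the study will include data from 20 patients who have IRE as standard of care, section 14.1 assesses patency after IRE treatment, and there is no randomisation to protect. No section says IRE would be abandoned for placement reasons: a metal stent is expressly not a contraindication, and section 9.0 plans repeated ablations until the whole tumour area is covered. An arrhythmia during IRE illustrates partial delivery, which the pulse percentage already captures.

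Much of this stands. It supports keeping 20 treated patients for the decision rules, and it means non-delivery may be rare. It does not answer the completion point, because an outcome that measures whether IRE could be carried out cannot sensibly be restricted to those in whom it was.

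It is also fair to say that 20/20 against 20/21 is a delivery rate, and that scoring no delivery as 0% is an added convention. It is the natural one for a percentage of planned pulses.

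Two stronger readings are tempting, and the documents support neither:

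- **That the 30-day safety result is biased favourably.** Section 1.0 defines the complications as IRE-related and section 14.1 counts them after IRE, so a patient without IRE falls outside the definition. Each such patient is also replaced by one who can have an event. The bias would be favourable only if undelivered patients had more complications than treated ones, for example if delivery failed because of an intraoperative event.
- **That patency is overstated by a known amount.** Dividing the successes by 20 + k assumes that every undelivered patient fails. These patients may still be drained or stented, and patency is timed from the IRE procedure, so it is undefined for them.

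**Conclusion.** The concern holds for the completion outcome. Sections 10.0 and 14.1 exclude its worst result by rule, so it is overstated whenever an eligible patient is opened for IRE and receives no pulses. For 1, 2 or 3 such patients the overstatement is 4.8, 9.1 or 13.0 points if all 20 treated patients complete. Those counts are assumptions, and the documents do not allow the actual size to be estimated.

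For safety the finding is narrower: the operative complications of these patients have no defined place in the results, and the effect on the rate could go either way. The primary patency rule is not affected. Excluding patients found resectable or disseminated at exploration is a matter of eligibility and is not criticised.

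**What to change.** In sections 10.0 and 14.1:

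1. Limit screen failure and replacement to patients who do not reach the operating room or who are found ineligible at exploration.
2. Define IRE as attempted once eligibility is confirmed at exploration and IRE is intended.
3. Include every attempted patient in the completion outcome, with the actual percentage of planned pulses, or 0% if none are given.
4. List non-delivery by reason, and report 30-day complications of attempted but untreated patients beside the treated set.
5. State that the patency rule and the 4-of-8 and 6-of-20 safety boundaries remain based on treated patients, with 20 treated in total.

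The cost is protocol wording, 30-day follow-up of a few patients already in postoperative care at the centre, and a completion rate that may look slightly less favourable. Sample size and decision rules do not change.

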15.1 RESEARCH PARTICIPANT REGISTRATION AND RANDOMIZATION PROCEDURES

15.2 Research Participant Registration

Confirm eligibility as defined in the section entitled Criteria for Patient/Subject Eligibility.

Obtain informed consent, by following procedures defined in section entitled Informed Consent Procedures.

During the registration process, individuals will be required to complete a protocol specific Eligibility Checklist.

The individual signing the Eligibility Checklist will confirm whether or not the participant is eligible to enroll in the study. Study staff are responsible for ensuring that all institutional requirements necessary to enroll a participant to the study have been completed. See related Clinical Research Policy and Procedure #401 (Protocol Participant Registration).

All participants must be registered through the Clinical Trial Management System (CTMS). The completed signature page of the written consent/RA or verbal script/RA, a completed Eligibility Checklist and other relevant documents must be uploaded into CTMS.

152 Randomization

Not applicable

161 DATA MANAGEMENT ISSUES

A Clinical Research Coordinator (CRC) will be assigned to the study. The responsibilities of the CRC include project compliance, patient registration, eligibility confirmation, data collection, abstraction and entry, data reporting, sample de-identification, regulatory monitoring, problem resolution and prioritization and coordination of the activities of the protocol study team. The data collected for this study will be entered into a REDCap database on a secure server.

162 Quality Assurance

Weekly registration reports will be generated to monitor patient accruals and completeness of consent and registration data. Routine data quality reports will be generated to assess missing data and inconsistencies. Accrual rates and extent and accuracy of evaluations and follow-up will be monitored periodically throughout the study period and potential problems will be brought to the attention of the study team for discussion and action. The principal investigator will maintain final responsibility for data during the study and during the final analysis of data. Breaches of protocol, problems with informed consent, or discrepancies in data accuracy will be reported to the IRB as required.

163 Data and Safety Monitoring

The Data and Safety Monitoring (DSM) Plans at Memorial Sloan Kettering Cancer Center were approved by the National Cancer Institute in September 2001. The plans address the new policies set forth by the NCI in the document entitled "Policy of the National Cancer Institute for Data and Safety Monitoring of Clinical Trials" which can be found at:

<http://www.cancer.gov/clinicaltrials/conducting/dsm-guidelines>. The DSM Plans at MSKCC

were established and are monitored by the Office of Clinical Research. The MSKCC Data and Safety Monitoring Plans can be found on the MSKCC Intranet at:

<https://one.mskcc.org/sites/pub/clinresearch/Documents/MSKCC%20Data%20and%20Safety%20Monitoring%20Plans.pdf>

There are several different mechanisms by which clinical trials are monitored for data, safety and quality. There are institutional processes in place for quality assurance (e.g., protocol monitoring, compliance and data verification audits, therapeutic response, and staff education on clinical research QA) and departmental procedures for quality control, plus there are two institutional committees that are responsible for monitoring the activities of our clinical trials programs. The committees: *Data and Safety Monitoring Committee (DSMC)* for Phase I and II clinical trials, and the *Data and Safety Monitoring Board (DSMB)* for Phase III clinical trials, report to the Center's Research Council and Institutional Review Board.

16.3 Regulatory Documentation

Prior to implementing this protocol at I'v1SK, the protocol, informed consent form, HIPAA authorization and any other information pertaining to participants must be approved by the MSK Institutional Review Board/Privacy Board (IRB/PB). There will be one protocol document and each participating site will utilize that document.

17.1 PROTECTION OF HUMMI SUBJECTS

The responsible investigator will ensure that this study is conducted in agreement with the Declaration of Helsinki (Tokyo, Venice, Hong Kong, Somerset West and Edinburgh amendments). The study will seek in every way to protect the rights of human subjects. The potential risks will be discussed in detail with the patients. Potential side effects as outlined above will be discussed with the patients. No patient will be required to participate in the study and participation or lack of participation will not affect the patient's subsequent care or treatment. The cost of getting the RE procedure is not paid by the study sponsor, so the patient or their insurance company will have to pay for this. Participation will be purely voluntary and subjects will not be reimbursed for participation in the study. Throughout the study, patient confidentiality will be maintained. No results of the study will be presented or discussed in a fashion that will allow identification of a particular patient in the study. All adverse events (AEs) will be fully disclosed to the IRB in a timely fashion as required.

17.2 Privacy

MSK's Privacy Office may allow the use and disclosure of protected health information pursuant to a completed and signed Research Authorization form. The use and disclosure of protected health information will be limited to the individuals described in the Research Authorization form. A Research Authorization form must be completed by the Principal Investigator and approved by the IRB and Privacy Board (IRB/PB).

The consent indicates that individualized de-identified information collected for the purposes of this study may be shared with other qualified researchers. Only researchers who have received approval from MSK will be allowed to access this information which will not include protected health information, such as the participant's name, except for dates. It is also stated in the Research Authorization that their research data may be shared with other qualified researchers.

17.3 Serious Adverse Event (SAE) Reporting

An adverse event is considered serious if it results in one of the following outcomes:

- Death
- A life-threatening adverse event
- An adverse event that results in inpatient hospitalization or prolongation of existing hospitalization
- A persistent or significant incapacity or substantial disruption of the ability to conduct normal life functions
- A congenital anomaly/birth defect

- Important Medical Events (IME) that may not result in death, be life threatening, or require hospitalization may be considered serious when, based upon medical judgment, they may jeopardize the patient or participant and may require medical or surgical intervention to prevent one of the outcomes listed in this definition

Note: Hospital admission for a planned procedure/disease treatment is not considered an SAE.

SAE reporting is required as soon as the participant starts investigational treatment/intervention. SAE reporting is required for 30-days after the participant's last investigational treatment/intervention. Any event that occurs after the 30-day period that is unexpected and at least possibly related to protocol treatment must be reported.

Please note: Any SAE that occurs prior to the start of investigational treatment/intervention and is related to a screening test or procedure (i.e., a screening biopsy) must be reported.

All SAEs must be submitted in PIMS. If an SAE requires submission to the HRPP office per IRB SOP RR-408 'Reporting of Serious Adverse Events', the SAE report must be submitted within 5 calendar days of the event. All other SAEs must be submitted within 30 calendar days of the event.

The report should contain the following information:

- The date the adverse event occurred
- The adverse event
- The grade of the event
- Relationship of the adverse event to the treatment(s)
- If the AE was expected
- Detailed text that includes the following
 - An explanation of how the AE was handled
 - A description of the participant's condition
 - Indication if the participant remains on the study
- If an amendment will need to be made to the protocol and/or consent form
- If the SAE is an Unanticipated Problem

For IND/IDE protocols: The SAE report should be completed as per above instructions. If appropriate, the report will be forwarded to the FDA by the IND Office

172.1

Any additional SAE reporting information required by the sponsor or drug supplier should be included in this section.

